ISO 14155:2011 also specifies general requirements intended to protect the rights, safety and well-being of human subjects, ensure the scientific conduct of the clinical investigation and the credibility of the results, define the responsibilities of the sponsor and principal investigator, and assist sponsors, investigators, ethics committees, regulatory authorities and other bodies involved in the conformity assessment of medical devices.

MEDDEVs are guidelines aiming at promoting a common approach by manufacturers and notified Bodies involved in the conformity assessment procedures according to the relevant annexes of the directives and by the competent authorities' charged with safeguarding public health, etc.

Osteolysis - pathological destruction or disappearance of bone tissue.

Subsidence - sinking or settling in bone, as of a prosthetic component of a total joint implant.

PROTOCOL SYNOPSIS

Study Title	UK Post-Market Clinical Follow-Up Of The INFINITY® Total Ankle System
Study Design	Prospective, multi-site, multi-year post-market clinical follow-up study
Study Group	Primary/Unilateral and/or bilateral Total Ankle Arthroplasty subjects implanted with INFINITY® Total Ankle System
N Subjects	500 with 12 sites
Follow-Up Schedule	Subject enrollment will consist of a Pre-operative, Operative, 6 months, 1 yr., 2 yr., 5yr., 7 yr., 10 yr., and an unscheduled visit as needed.
Primary Objective	Evaluate the long-term survivorship of the INFINITY® implant over 10 years
Secondary Objective(s)	
Secondary objectives assessed will be to:
 
 • Identify and assess the implant for component loosening and/or subsidence, any osteolysis and/or cyst formation through radiographic evaluation early and throughout the lifetime of the implant. • Compare the improvements in self-reported pain and social interaction for quality of life measures from pre-op through 10 years post operatively; assessed by EuroQol (EQ5D5L). • Compare pain and functional improvement in the Ankle Osteoarthritis Score (AOS), which is a visual analogue scale specifically designed as a modification of the Foot Function Index. • Compare the improvement in self-reported pain-free function scores from pre-op through 10 years post-operatively, assessed by the Manchester Oxford Foot Questionnaire (MOXFQ) walking/standing scores. • Identify and report the safety of the implant in terms of complications and adverse events.

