Inclusion Criteria	
Subjects to be included in the study must meet all of the following criteria:
 
 • Be 21 years of age at the time of surgery; • Diagnosed with unilateral and/or bilateral ankle joint disease; • Diagnosed with ankle joint damage from rheumatoid arthritis, post-traumatic, or degenerative arthritis; • Willing and able to consent to participate (written, informed consent / witnessed verbal consent) • Willing and able to attend the requested follow-up visits; • Subjects determined by the Investigator to be an appropriate candidate for the INFINITY® Total Ankle System
Exclusion Criteria	
Subjects will be excluded from the study if they meet any of the following criteria:
 
 • Subjects with an ankle condition, as determined by the investigator, to be an inappropriate candidate for a total ankle replacement; • Subjects requiring revision total ankle replacement of the ankle being considered for study

SCHEDULE of EVENTS

Procedures	Pre-op	Op.	6 mo +/-30 days	1 yr +/-60 days	2 yr +/-60 days	5 yr +/-60 days	7 yr +/-60 days	10 yr +/-60 days	Study Close
Informed Consent	X								
Inclusion/Exclusion Criteria	X								
Medical History/Demographics	X								
Operative (Surgical) procedure/device		X							
EQ5D5L	X		X	X	X	X	X	X	
Ankle Osteoarthritis Score (AOS)	X		X	X	X	X	X	X	
Manchester-Oxford Foot Questionnaire	X		X	X	X	X	X	X	
Radiographic Assessment (Investigator requirement) ¹	X		X	X	X	X	X	X	
Adverse Event Assessment		X	X	X	X	X	X	X	
End of Study									X
Surgical Intervention ²									
*Sponsor-approved Unscheduled Visit ³									

¹Standard Clinical Care Radiographic assessment (X-Rays) will be collected annually as part of standard clinical care. No research specific X-rays will be taken during the study.

²&³ These are not scheduled time point events but will be observed for throughout study participation.

INTRODUCTION

Wright Medical introduced the INFINITY®, a CE Marked total ankle system, for use in total ankle arthroplasty replacement (TAR) in the United States, Canada, and Europe, including the UK in 2014. The INFINITY® Total Ankle System is a fixed-bearing, bone-sparing total ankle prosthesis that restores mobility to a failing ankle joint. It encompasses three components (i.e., tibial tray, tibial insert, and talar dome).

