Planned visits and Follow-Up Time Points

Subjects will be seen prospectively at the following intervals Pre-Op, Operative, 6 months, 1, 2, 5, 7, and 10 years. If there are special circumstances where the subjects require a visit outside the windows of the established visits, the investigator may seek approval from Wright Medical for an acceptance of an “unscheduled visit” and it will be determined if the data will be included and analyzed.

SITE/SUBJECT SELECTION

Clinical Research Sites will be identified to participate in the study based on current experience, and training in the use of the INFINITY® Total Ankle System and according to ICH GCP guidelines and ISO 14155: 2011 which states; qualified by education, training and experience to perform his or her respective task(s). It is the expectation the surgeon will adhere to and follow the INFINITY® Surgical Technique and have knowledge of the contraindications as provided in the Instructions for Use (IFU). (See Appendix A).

Study Design Summary

Informed Consent

Subjects will be recruited based on interest in participating in the study. All subjects will be consented by an appropriately trained clinician or research nurse using the REC approved information sheet and consent form in order to participate in the study and prior to any data collection, or any study procedure. The study clinician or research nurse will assess whether the patient can give informed consent or not during the consent process, in compliance with the 2005 Mental Capacity Act. The potential participant must be allowed ample time to review the informed consent and should be allowed to take the time to read, review, ask questions, and receive answers as well as being fully informed of all aspects of the study before a decision is made to participate. The source documentation will include a statement of the consent process and include details of the person taking consent for study participation.

Screening

Subjects with interest in participating in the study, after signing the informed consent document, will then be invited to participate if they meet the Inclusion Criteria.

Point of Enrollment

Subjects will be considered enrolled in the study when they have:

- Been informed of all aspects of the study and have signed or have their verbal consent witnessed on the Informed Consent document
- Acknowledged the appropriate patient data release information (included in the Informed Consent document)

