- Satisfied the Inclusion/Exclusion Criteria
- Implanted with the Device

Investigators should document subject enrollment by completing the screening and enrollment logs located within the trial master file. The Source documentation should clearly state that all inclusion and exclusion criteria have been met and the patient data release and informed consent documents have been signed and appropriately dated prior to any study related activity,

The investigative sites will be assigned three digit a site code ***, and at enrollment the subject will be assigned a sequential subject identification number corresponding to the order the subject was enrolled (i.e. the first subject enrolled at each site will be site number *** followed by subject identifier 001). The assigned codes will be used to identify the subject on all case report forms. All investigative sites will be provided protocol training of the during the site initiation visits. Investigative sites will be provided paper case report forms/booklets, which may be used as source documentation, these must signed by the individual completing the form; i.e., coordinator, patient, or investigator.

Study Duration, Subject Participation and Estimated Enrollment Period

The total study duration from , first patient, first visit, (FPFV) to last patient, last visit (LPLV) is expected to be 13 years, with a recruitment period of 36 months The investigator/investigative site must make every reasonable attempt to contact the patients to complete all scheduled post-operative visits within the visit window. In instances where the individual cannot be reached, the investigator/investigative site will document at least two attempts to contact the

patient via phone/mail and one certified letter for each time point. Due to the length of this study and the risk of lost to follow-up potential, if a subject has an inability to and, for some unforeseen reason cannot be seen on the hospital site, patient reported outcome measure case report forms may be completed remotely by post or telephone and returned to the investigative site/investigator for review and submission. If this process is applied it must be documented and reported to Wright accordingly.

Subject Withdrawal or Discontinuation

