Subjects maintain the right to discontinue their participation in the study at any point without penalty or loss of benefit to which the subject is otherwise entitled per ICH E6 4.8.10(m) guidelines. Although, a subject is not obliged to give his or her reason(s) for withdrawing prematurely from this study, the investigator should make a reasonable effort to ascertain the reason(s), while fully respecting the subject's rights per ICH E6 4.3.4 guidelines.

Device Failure

Subjects will be considered a treatment failure, and will be withdrawn from the study if any sections of the device (tibial or talar metal components) have been removed at any time during their participation. This should be reported onto the adverse event form. In addition, any surgical intervention during study participation that relates to their total ankle replacement will be reported on the surgical intervention case report form.

Procedures and Case Report Forms

Subject medical history and demographic information will be collected and recorded onto the demographic case report form. The following information will be collected on these forms:

- Date of birth
- Gender
- Height
- Weight
- BMI calculation
- Smoking status
- Status of other joints that affect ambulation (i.e., knee replacement, contralateral arthritis and/or ankle replacement)
- Concomitant health conditions (diabetes and other medical conditions, etc.)

Operative Procedure Information

The information related to the subject's operation will be collected and recorded according to the Operative Information Case Report Forms. The following operative information related to the primary TAR procedure will be documented on these forms:

- Primary diagnosis
- Any previous surgery to index joint
- Date of operation
- Site location
- Surgical approach
 - Instrumentation type (standard) or (additional approved INFINITY® instrumentation)

- List concomitant operative procedures such as tendon/deltoid lengthening or other reconstructive process required to make final implantation correct
- Cement use
- Intraoperative complications (to be collected on the Adverse Event Case Report Form)
- Product description and eight-digit product code for all components implanted

Patient Reported Outcome Measures (PROMS)

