- intra-articular ankle varus or valgus alignment was defined as the angle of the proximal talar surface (talar tilt) to the lateral border of the tibia in the distal diaphysis and metaphyseal region more than 10 degrees on the AP weightbearing ankle views
- Type 3: Ankle arthritis with hindfoot deformity, tibial malunion, midfoot abductus or adductus, supinated midfoot, plantar flexed first ray, etc.
- hindfoot deformity defined as the angle between the lateral border of the calcaneus and the long axis of the tibia on the AP view of the ankle (varus more than 5 degrees, valgus more than 10 degrees)
- Tibial deformity defined as an angulation between the lateral border of the tibia more than 10 degrees on the AP view of the ankle **

Type 4: Types 1, 2, and 3 plus subtalar, calcaneocuboid, or talonavicular arthritis **

The post-operative radiographic evaluations will be to assess, record, and report migration, loosening, subsidence of the device, any osteolysis and cyst formation.

Notes:

* Greater than 10 degrees (defined as the angle between a line perpendicular to the anatomical axis of the tibia and a line drawn along the top of the talar dome (see figure) and recorded as either varus or valgus

** If the patient has required staged surgical deformity as part of the management of the ankle arthritis (within 18 months of TAR), this should be considered a type 3. However, if the patient has undergone historic corrective surgery then the current foot position should be used for the purpose of COFAS grading (ie, if fully corrected and then can be Grade I).

*** this would include patients with prior arthrodesis of the subtalar, calcaneocuboid, or talonavicular joints.

STATISTICAL CONSIDERATION

Sample Size

The total sample size is 500 subjects. The sample size was not calculated using statistical methods. A non-parametric statistical analysis for survivorship using the Kaplan-Meier will be applied to determine the implant survivorship.

This total sample size is based on historical knowledge and a precedent being set for the UK by “The Orthopaedic Data Evaluation Panel” (ODEP) ratings for arthroplasty implants. Mechanical survivorship for total hip and knee replacement is currently thought to be approximately 10 years. This benchmark for long-term data collection is not only

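### The Device Failure rule withdraws the whole subject when one ankle loses a metal component, so in a bilateral subject it also ends follow-up of a working contralateral study implant

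*Protocol*

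**What the plan says.** The Protocol Synopsis defines the study group as "Primary/Unilateral and/or bilateral Total Ankle Arthroplasty subjects implanted with INFINITY® Total Ankle System". An inclusion criterion reads "Diagnosed with unilateral and/or bilateral ankle joint disease". The primary objective is "Evaluate the long-term survivorship of the INFINITY® implant over 10 years", and under Sample Size the Kaplan-Meier method "will be applied to determine the implant survivorship". In all of these the object of interest is the implant.

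The operating rules are set per subject:

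- **Failure and withdrawal** (Device Failure): "Subjects will be considered a treatment failure, and will be withdrawn from the study if any sections of the device"; the condition is completed by removal of tibial or talar metal at any time during participation.
- **Visits** (Planned visits and Follow-Up Time Points): the calendar is a single series, given as "Subjects will be seen prospectively at the following intervals Pre-Op, Operative, 6 months, 1, 2, 5, 7, and 10 years".
- **Identifier** (Point of Enrollment): "the subject will be assigned a sequential subject identification number corresponding to the order the subject was enrolled".
- **Completion** (Subject Completion): reached when the subject has finished all visits.
- **Adverse events** (Adverse Event Status Updates): follow-up stops, at the latest, when the subject's participation ends.

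No section exempts a second study ankle from the withdrawal rule, and none says that a bilateral subject has only one study ankle.

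**The concern.** A survivorship study needs each implant followed until it fails or until its planned end. If a bilateral subject has two study implants and one fails, the other is still at risk and still informative about long-term survival, radiographic loosening and safety. The withdrawal rule stops its visits, radiographs, questionnaires and adverse event follow-up on the day its neighbour fails.

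The cut-off is tied to an event in the same patient, so it need not be independent of the remaining implant's own risk. A statistical analysis plan can choose the unit of analysis or allow for clustering. It cannot supply observations that the protocol told sites to stop making, and the protocol describes no data collection after withdrawal. The point therefore belongs in the protocol.

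**Working it through.** **Figure in the plan.** The 13-year duration reproduces: 36 months / 12 + 10 years = 13 years. An ankle implanted at any time in the recruitment period can thus reach 10 years within the study. The figure of 500 subjects cannot be reproduced, because the protocol states that it was not calculated.

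**Inputs.** From the protocol: N = 500 subjects. Assumed, since the protocol gives neither: bilateral share b = 2% to 10%; 10-year failure risk per ankle q = 10%; both ankles implanted together; independent ankles with a constant hazard.

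**Implants lost early.**

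- Bilateral subjects: 500 × 0.02 = 10, to 500 × 0.10 = 50.
- Exactly one ankle fails within 10 years: 2 × 0.10 × 0.90 = 0.18. Working implants withdrawn that would have lasted 10 years: 10 × 0.18 = 1.8, to 50 × 0.18 = 9.0.
- At least one ankle fails: 1 − 0.90² = 0.19. All contralateral implants cut off, including those that would have failed later unseen: 10 × 0.19 = 1.9, to 50 × 0.19 = 9.5.
- Later failures not observed: 10 × 0.10² = 0.1, to 50 × 0.10² = 0.5.

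**Implant-years lost.** With hazard λ = −ln(0.90)/10 = 0.01054 per year, the expected loss per bilateral subject is q²/λ = 0.01/0.01054 = 0.949 years. That is 9.5 years for 10 subjects and about 47.5 for 50. Expected time at risk per implant over 10 years is q/λ = 9.49 years. The loss is therefore 9.5/(510 × 9.49) = 0.2% to 47.5/(550 × 9.49) = 0.9% of all implant-years.

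**Wider range.** The number cut off is 500 × b × [1 − (1 − q)²]:

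| b | q = 5% | q = 10% | q = 20% |
|---|---|---|---|
| 2% | 1.0 | 1.9 | 3.6 |
| 5% | 2.4 | 4.7 | 9.0 |
| 10% | 4.9 | 9.5 | 18.0 |
| 20% | 9.8 | 19.0 | 36.0 |

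**Effect on the estimate.** A per-ankle Kaplan-Meier analysis was simulated with the withdrawal rule applied as censoring, true 10-year survival 0.900 and b = 5%, 10% and 20%. Correlation within a subject came from a shared gamma frailty.

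| Frailty variance | b = 5% | b = 10% | b = 20% |
|---|---|---|---|
| 0 (independent) | 0.8996 | 0.8996 | 0.9004 |
| 1 | 0.9007 | 0.9008 | 0.9016 |
| 2 | 0.9010 | 0.9014 | 0.9031 |

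For scale, the binomial standard error at 90% with 500 independent units is √(0.9 × 0.1/500) = 0.013. The largest shift, 0.003, is under a quarter of that.

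**The case against.** The strongest reply is that the protocol may intend one study ankle per subject. The exclusion criterion on revision refers to a single ankle under consideration, the operative section asks about earlier surgery to the index joint, and contralateral ankle replacement is listed with medical history as the status of another joint. The inclusion criterion admits bilateral disease, which is not the same as two study implants. On that reading, withdrawal ends no study implant's follow-up. The reading is possible, but it is nowhere stated, and it leaves the bilateral arthroplasty group in the synopsis unexplained. Either way a sentence is missing.

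The second reply is that the bias is negligible. That stands. The case rests on lost follow-up, not on a distorted survival curve.

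A reader might also infer three stronger points that the document does not support:

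- **That a staged second implant is denied a 10-year schedule.** The protocol is silent: it neither bars a second enrolment or calendar nor provides one. An ankle implanted after the 36-month recruitment period has no clear claim to be a study implant.
- **That questionnaires completed after contralateral surgery will be read as results of the first ankle.** No such rule is written. How those visits are handled is an analysis choice that the statistical analysis plan, not shown here, may settle.
- **That survivorship will be counted per subject, inflating the failure rate.** The objective and the Kaplan-Meier sentence both name the implant.

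**Conclusion.** The point holds in a limited form. The protocol admits bilateral arthroplasty subjects and makes implant survivorship its primary question, yet its failure rule removes the whole person. Followed literally, the rule discards follow-up of a functioning contralateral study implant, and this cannot be repaired at the analysis stage.

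The size is modest: about 2 to 9 implants at 2% to 10% bilateral, 10% failure per ankle and independence, or about 1 to 36 over the wider assumed ranges. The bias in 10-year survival is at most about 0.3 percentage points in the settings simulated. The bilateral share drives these figures, and the protocol does not give it. If only one ankle per subject was ever meant to be studied, the loss is nil and what remains is an unstated unit. The rule should be corrected, because the correction is cheap and the study exists to collect long-term implant data. It does not threaten the primary analysis.

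**What to change.** Amend Device Failure to say that removal of a metal component is a failure of that ankle, that it ends study follow-up for that ankle only, and that the subject stays in the study for any other study ankle. Record side and operation date for each study ankle implanted within the recruitment period. The operative data listed include the operation date but do not plainly name the side; the forms themselves are not shown and may already capture it.

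Alternatively, state that only the first implanted ankle is the study ankle for the primary endpoint. That settles the unit without extending anyone's follow-up.

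The first option costs amendment wording, a side field if none exists, and a few extra visits for a small number of bilateral subjects. Limiting it to ankles implanted during recruitment keeps it within the planned 13 years. The second option costs one sentence but gives up primary-endpoint information on second ankles.

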relevant to the safety and survivorship of the implant but, also to provide assurances that for the introduction of new implants, a data collection plan is in place for ongoing evaluations and reporting.

The information gained from this data collection will be analyzed at times based on potential publication periods around 3, 5, and 7 years with a final analysis after all subjects have completed all follow-up requirements at the 10 year final visit. In addition, at time points determined by the investigators and/or Wright Medical will be evaluated as needed or required for additional analysis of data for reporting and/or publication purposes will be done throughout the study.

Demographics

Descriptive statistics will be applied for the demographic data of all subjects. Pre to post-operative comparisons will be made for all outcome measures at the specific data collection time points. Summary statistics for continuous variables may include subject count, mean, standard deviation, minimum and maximum values.

ADVERSE EVENTS

Suspected Unexpected Serious Adverse Reactions (SUSARS), Serious Adverse Events (SAE's) & ADVERSE EVENTS (AE's)

Procedural and device related events will be described and collected on the AE form. It is the responsibility of the operating surgeon/s to be aware and note the adverse effects from the package insert/instructions for use by the manufacturer/sponsor. (See appendix A) The number of subjects experiencing each adverse event percentage or proportion of the total number of subjects experiencing each adverse event will also be reported. All adverse events shall be reported in an interim and/or final report of the clinical investigation. All device deficiencies related to the identity, quality, durability, reliability, safety or performance of the investigational medical device shall be documented throughout the clinical investigation and appropriately managed by the sponsor.

Potential intraoperative and early postoperative complications, related to all total ankle replacements may include:

- pain;
- sudden drop in blood pressure intra-operatively due to the use of bone cement;
- damage to blood vessels;
- temporary or permanent nerve damage resulting in pain or numbness of the affected limb;
- cardiovascular disorders including venous thrombosis, pulmonary embolism, or myocardial infarction.
- hematoma;
- delayed wound healing; and
- deep wound infection (early or late) which may necessitate removal of the prosthesis.

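### For late complications, the stated adverse-event measure (a crude proportion of all subjects) has no time horizon and falls below the cumulative risk when follow-up is unequal or incomplete

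*Protocol*

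**What the plan says.** The Adverse Events section of the protocol names two summaries: the number of subjects with each event, and a percentage or proportion, in the words "proportion of the total number of subjects experiencing each adverse event will also be reported". The sentence is garbled, but subjects with the event over all subjects is its natural reading. The section adds: "All adverse events shall be reported in an interim and/or final report of the clinical investigation".

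The timing comes from elsewhere in the protocol:

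- Study Duration, Subject Participation and Estimated Enrollment Period: the whole study "is expected to be 13 years", of which recruitment takes the first 36 months. The same section acknowledges that subjects may be lost to follow-up.
- Planned visits and Follow-Up Time Points: post-operative visits at "6 months, 1, 2, 5, 7, and 10 years".
- Statistical Consideration: data will be "analyzed at times based on potential publication periods around 3, 5, and 7 years". The last analysis waits until everyone has reached the 10-year visit, and further analyses may be done as needed.
- Device Failure: a subject whose tibial or talar metal component is removed is withdrawn.

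Kaplan-Meier is named for implant survivorship only (Primary and Secondary Endpoints; Sample Size). Safety is a named secondary endpoint.

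**The concern.** A crude proportion counts every subject in the denominator as if fully observed. A subject operated on last month, lost in year 2 or withdrawn in year 4 contributes the same as one followed for 10 years. Events of the first weeks are hardly touched by this. Complications that build up over years are: fracture, loosening, late infection, re-operation. The protocol's own list of risks includes a group of late complications.

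The primary endpoint is estimated with a method that allows for censoring, while the safety percentages beside it are not. A reader of a report at year 3 or 5 would see a survivorship figure tied to a time since surgery and complication percentages tied to none. Percentages in successive reports would also not be comparable, because the follow-up behind them differs. The results are meant for regulators, notified bodies and publication, on a device for which the protocol says little has been published.

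**Working it through.** **Inputs from the protocol.** Accrual 36 months, 10 years of follow-up per subject, looks around 3, 5 and 7 years, final analysis after the last 10-year visit. The one stated figure that can be reproduced is the duration: 3 + 10 = 13 years, as stated.

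**Inputs that are assumptions.** The protocol gives no event or loss rates. Taken here: 10-year risk of a late complication 10% at constant hazard, so λ = −ln(0.90)/10 = 0.01054 per year; uniform entry over 3 years; loss of 0%, 2% or 5% per year, unrelated to the event, as a hazard μ = −ln(1 − loss), that is 0, 0.0202 or 0.0513.

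**Formulas.** For a subject with potential follow-up f, the probability that an event is observed is λ/(λ+μ) × [1 − exp(−(λ+μ)f)]. The crude proportion at calendar time T averages this over entry times e from 0 to 3, with f = min(T − e, 10). The comparator is the cumulative risk 1 − exp(−λ·min(T, 10)).

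**Looks by calendar time from the first patient.**

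| Look | Mean potential follow-up | Cumulative risk | Crude, no loss | Crude, 2%/yr | Crude, 5%/yr |
|---|---|---|---|---|---|
| Year 3 | 1.5 yr | 3.11% | 1.56% (0.50) | 1.53% (0.49) | 1.49% (0.48) |
| Year 5 | 3.5 yr | 5.13% | 3.62% (0.70) | 3.49% (0.68) | 3.30% (0.64) |
| Year 7 | 5.5 yr | 7.11% | 5.63% (0.79) | 5.32% (0.75) | 4.89% (0.69) |
| Final (13) | 10 yr | 10.0% | 10.0% (1.00) | 9.07% (0.91) | 7.86% (0.79) |

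Ratios of crude to cumulative risk are in brackets. Check of the first cell: 1 − [1 − exp(−3λ)]/(3λ) = 1 − 0.03111/0.03161 = 1.56%. Check of the last: 0.01054/0.06183 × [1 − exp(−0.6183)] = 0.1704 × 0.4611 = 7.86%. With 10-year risks of 5% and 20% the ratios are almost the same (0.50 and 0.51 at year 3 without loss).

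**Looks by time since surgery.** Every subject then has the same potential follow-up and only loss acts. At 3, 5 and 7 years the ratios are 0.97, 0.95 and 0.93 with 2% loss a year, and 0.93, 0.88 and 0.84 with 5%.

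**Early complications.** Take a 10% risk spread evenly over an assumed 90 days (0.25 year). At calendar year 3 only those operated on in the last quarter-year are partly observed, on average half, so the ratio is 1 − (0.25/2)/3 = 0.96. From year 5 on it is 1.00.

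**The case against.** The strongest reply is that a count and a percentage correctly describe what was observed. The protocol never calls the percentage a 3-, 5- or 10-year risk, the wording excludes no further summaries, and exposure-adjusted tables are often left to a statistical analysis plan, which was not available here. This stands in part: the percentage misleads only when read as a risk. But the protocol chose this measure itself and named no other besides the count, so a plan that merely followed it would give late-event percentages without horizon or exposure.

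The interim comparator is also open to challenge. At calendar year 3 almost nobody has 3 years of follow-up, so no method could estimate the 3-year risk well then. Set against the risk at mean follow-up the gap disappears: 1 − exp(−λ × 1.5) = 1.57% against a crude 1.56%. This stands too. It means that the follow-up time must appear beside the percentage, and that any cumulative incidence must stop where the numbers at risk become small.

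A reader might infer that complication risks in general will be understated, and always in the device's favour. The documents do not support that:

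- Intraoperative and early events, many of which the protocol lists, are almost unaffected.
- At the final analysis staggered entry contributes nothing.
- The protocol does not say whether the looks are by calendar time or by time since surgery, nor that adverse events appear in every interim report.
- Death and component removal are competing events. Treating them as ordinary censoring would overstate risk.

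Component removal itself counts as device failure, and implant survivorship already has Kaplan-Meier.

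**Conclusion.** The point holds for late complications only. The proportion named in the protocol has no common time horizon, and for these events it lies below the cumulative risk when follow-up is unequal or incomplete.

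The largest effect is at interim looks by calendar time: about 0.5, 0.7 and 0.8 of the 3-, 5- and 7-year risk, given uniform accrual, constant hazard and no loss. If the looks are by time since surgery, the shortfall is that of loss alone. At the final analysis it depends wholly on loss, whose rate the protocol does not give: none at zero loss, about 9% to 21% of the risk at an assumed 2–5% a year.

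This is a cheap improvement to a secondary safety summary. It does not touch the survivorship endpoint, and it does not show that the crude figures are wrong as descriptions.

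**What to change.** In the same paragraph of the Adverse Events section:

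1. Repair the sentence so that the numerator and denominator are clear. Keep the counts and percentages, and state the follow-up time beside them (for example mean or median, and total patient-years).
2. For key late complications, such as fracture, loosening, late infection and re-operation, add the cumulative incidence of first event at fixed times since surgery. Limit it to horizons with adequate numbers at risk, show those numbers, and treat death and component removal as competing events where they are not themselves the event. Rates per 100 patient-years may be given as well or instead.
3. State that interim crude percentages are not to be presented as fixed-horizon risks.

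The cost is a short addition to the text and a few extra tables. Operation dates are already collected, and the survivorship analysis needs failure and last-follow-up dates anyway. The one thing to confirm is that the adverse-event form records the date of onset. The downside is that late-event figures will look less favourable than the crude percentages.
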